## **4.4. Pharmacokinetic and Immunogenicity Analyses**

### Pharmacokinetic Analysis

All PK data analysis will be conducted using the PKS.

For all patients, trough and post-treatment concentrations of ISIS 681257 in plasma (as total full length oligonucleotides, including fully conjugated, partially conjugated, and unconjugated ISIS 681257) will be determined and summarized by treatment with and without stratification by patient immunogenicity (IM) status using descriptive statistics. In addition, plasma terminal elimination half-life of ISIS 681257 will be calculated using the post-treatment follow-up data if data permits.

Additionally, for patients in the PK subgroup only, PK parameters will be calculated using non-compartmental methods. The maximum plasma concentration ( $C_{\max}$ ) and time to reach  $C_{\max}$  ( $T_{\max}$ ) values will be obtained directly from the plasma concentration-time data. The area under the plasma concentration-time curve (AUC) values after the first dose ( $AUC_{0-24h}$ ) and steady-state dose ( $AUC_{0-24h}$  and  $AUC_{\tau}$ ) will be calculated using the linear trapezoidal rule. Other PK parameters may be calculated at the discretion of the PK scientist. Plasma PK parameters will be summarized using descriptive statistics with and without stratification by patient IM status.

Exposure-response relationships between selected PD [e.g., Lp(a)] and PK measures (e.g., plasma trough concentrations) may be explored (with and without stratification by IM status) in this study, or in a separate population PK analysis combined with other clinical studies.

### Immunogenicity Analysis

All IM data analysis will be conducted using the Safety Set.

The IM of ISIS 681257 will be assessed before, during, and after treatment with Study Drug (ISIS 681257 or placebo). The IM incidence (number) and incidence rate (percent) will be summarized at each evaluated study time point and at the patient level by treatment and dose, as the total number of and percent of evaluated patients with antibody negative, positive, and unknown status. Subject IM status (positive/negative or unknown) for all evaluable patients, along with the study day associated with the first positive IM status emerged (i.e., onset of ADA development), the last positive IM status observed ( $T_{\text{last}}$ ), and max and/or end of treatment titer will be listed by treatment group. Study patients with positive anti-ISIS 681257 antibody status may be qualitatively discussed as being either ‘persistent’, ‘transient’, or ‘not determinable’. Potential relationships of immunogenicity with selected efficacy, safety, and PK measures may be evaluated.

PK and IM sampling times will be provided in data listings.

## **4.5. Safety Analyses**

Safety analyses will be conducted primarily using the Safety Set population. The analyses may be reproduced on other populations if warranted.

#### 4.5.1. Study Drug Exposure

Study drug exposure will be calculated as the number of days patients were administered study drug, as determined below, and will be summarized by ISIS 681257 treatment group and pooled placebo group using descriptive statistics.

*Duration of Study Drug Exposure (days) = (Date of last dose – Date of first dose) + 1*

Duration of study drug exposure will also be presented in the following categories: ≤13 weeks, >13 to ≤26 weeks, >26 to ≤30 weeks, >30 to ≤34 weeks, >34 to ≤38 weeks, >38 to ≤42 weeks, >42 to ≤46 weeks, >46 to ≤50 weeks, and >50 weeks.

Percent compliance will be summarized for each patient from date of first dose through the treatment period per the following definition:

$$\text{Percent Compliance (\%)} = \frac{\text{Total Number of Infusions Received}}{\text{Total Number of Infusions Planned Per Protocol}} \times 100\%$$

Patient compliance with study drug will be summarized by treatment groups and pooled placebo group and presented in a by-patient data listing. For patients who withdrew/discontinued treatment early, the volume of study drug planned will be calculated based on the period on-treatment up to their withdrawal/termination.

The proportion of patients with compliance ≥ 80% and <80% will be calculated.

Total drug received will be summarized by treatment group and pooled placebo group. Actual dose intensity, defined as the ratio of total drug received and the actual duration of treatment (in weeks), and relative dose intensity, defined as the ratio of actual dose intensity and planned dose intensity, will be summarized by ISIS 681257 treatment group and pooled placebo group.

Duration of study drug exposure (in days and in weeks), percent compliance, total drug received, actual dose intensity and relative dose intensity for each patient will also be provided in data listings.

In addition to the Safety Set, all exposure analyses will be performed using the FAS as well.

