## 1.2. Study Design

### 1.2.1. Synopsis of Study Design

This is a multicenter, randomized, double-blind, placebo-controlled, dose-ranging study. ISIS 681257 (or placebo) will be administered subcutaneously (SC) every week, every 2 weeks, or every 4 weeks, depending on cohort assignment, for up to 52 weekly doses, up to 26 every 2-week doses, or up to 13 every 4-week doses. Minimum treatment duration is 6 months, maximum treatment duration is 12 months.

The primary analysis time point is at Week 25 for patients who received every 4-week dosing (Cohorts A-C) and at Week 27 for patients who received 2-week or weekly dosing (Cohorts D and E). For patients continuing treatment beyond the primary analysis time point additional supportive efficacy analysis (to evaluate whether the treatment effect is maintained) and safety analysis (for the purpose of dose(s) selection) will be repeated at the completion of Study Drug treatment. A description of each cohort is presented in [Table 1](#).

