**Table 1: Study Drug Dosing Information**

Cohort	Treatment	Volume to Administer/Dose	# Doses	Total ISIS 681257
A	20 mg ISIS 651257 or placebo (every 4 weeks)	0.2 mL	≤ 13	≤ 260 mg
B	40 mg ISIS 651257 or placebo (every 4 weeks)	0.4 mL	≤ 13	≤ 520 mg
C	60 mg ISIS 651257 or placebo (every 4 weeks)	0.6 mL	≤ 13	≤ 780 mg
D	20 mg ISIS 651257 or placebo (every 2 weeks)	0.2 mL	≤ 26	≤ 520 mg
E	20 mg ISIS 651257 or placebo (every week)	0.2 mL	≤ 52	≤ 1040 mg

The treatment portion of the study will be complete when the last enrolled patient reaches 6 months of exposure. All patients still on treatment will have their last dose taken as scheduled, and they will enter a 16-week post-treatment follow-up period at one dosing interval post last dose. Accordingly, for each treatment cohort treatment period is defined as the time from the first dose through one dosing interval post last dose.

Patients  $\geq 18$  and  $\leq 80$  years old with elevated plasma Lp(a) levels ( $\geq 60$  mg/dL ) and a clinical diagnosis of CVD are eligible for enrollment upon meeting the study specific eligibility criteria. Patients will be on standard-of-care preventative therapy for other than elevated Lp(a) CVD risk factors as per current guidelines.

Clinical diagnosis of CVD is defined as documented CAD, stroke, or PAD. A diagnosis of CAD has to be documented by any of the following:

- Angiographic evidence of  $\geq 50\%$  stenosis of 1 or more major epicardial coronary arteries.

- History of myocardial infarction documented by positive enzymes, and either symptoms of myocardial ischemia, or electrocardiogram (ECG) changes (Thygesen et al. 2012).
- History of coronary revascularization.
- Evidence of cardiac ischemia on exercise testing, or imaging study.

Patients will be evaluated for study eligibility during Screening, which takes place within 4 weeks prior to Day 1 (the first day of Study Drug administration). Patients who are determined to be eligible, based on screening assessments, will be enrolled in the study at Day 1 and randomly assigned to 1 of the 5 parallel dosing cohorts, with each cohort having a 5:1 ratio to receive ISIS 681257 or matching volume of placebo, respectively, by SC injection for up to 52 weeks.

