## **2. PATIENT POPULATION**

### **2.1. Population Definitions**

The following patient populations will be evaluated and used for presentation and analysis of the data:

- **Safety Set:** All patients who are randomized and receive at least 1 dose of Study Drug. This population will be used for all safety analyses.
- **Full Analysis Set (FAS):** All patients who are randomized and received at least 1 dose of Study Drug (ISIS 681257 or placebo). The FAS represents the practically-feasible intent-to-treat (ITT) population as delineated in International Conference on Harmonisation (ICH) Guideline E9. This population will be used for the primary analysis of efficacy.
- **Per-Protocol Set (PPS):** Subset of the FAS who have a baseline assessment for lipids, received within 6 months at least 5 out of 6 monthly doses of Study Drug for patients randomized in Cohorts A, B, and C, at least 11 out of 13 planned every-2-week doses for patients randomized in Cohort D, or at least 22 out of 26 planned weekly doses for patients randomized in Cohort E, and who have no major protocol deviations that would be expected to affect efficacy assessments. This population will be used for supportive inferences concerning efficacy.
- **Pharmacokinetic Set (PKS):** All patients who are randomized and received at least 1 dose of active Study Drug (ISIS 681257), and have at least 1 evaluable PK data. This population will be used for analysis of PK data.

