#### 4.5.2. Adverse Events

All AEs will be coded using the MedDRA v20.0 coding system and displayed in tables and data listings using system organ class (SOC) and preferred term. Missing and partial dates will be handled as described in [Section 3.10.2](#).

Analyses of AEs will be performed for those events that are considered treatment-emergent, where treatment-emergent is defined as any AE with onset after the first administration of study medication through the end of the study, or any event that was present at baseline but worsened in intensity or was subsequently considered drug-related by the Investigator through the end of the study.

All analyses of TEAEs will be performed on the following periods:

- TEAEs On Study, defined as any TEAE reported after onset of the administration of study medication through the end of the study
- TEAEs On Treatment, defined as any TEAE reported during treatment period defined as period from first dose through one dosing interval post last dose

Adverse events are summarized by patient incidence rates; therefore, in any tabulation, a patient contributes only once to the count for a given AE in both SOC and preferred term.

The number and percentage of patients with any treatment-emergent adverse event (TEAE), with any TEAE assessed by the Investigator as related to treatment (related, possible, unlikely/remove, and not related relationships), with any serious TEAE, and with any treatment-emergent serious AE potentially related to treatment will be summarized by ISIS 681257 treatment group and pooled placebo group. All incidences will also be summarized within each cohort, by ISIS 681257 and placebo.

In addition, AEs will be summarized by relationship to study drug and by severity. In these tabulations, each patient will contribute only once (ie, the most related occurrence or the most intense occurrence) to each of the incidence rates in the descriptive analysis, regardless of the number of episodes.

Three additional TEAE analyses will be performed:

1. Local cutaneous reaction at injection site (LCRIS) defined as either:
  - a. Moderate or severe Injection Site Erythema, Swelling, Pruritus, Pain or Tenderness that started on the day of injection, persisted for at least two days; or
  - b. Any AE at the injection site, regardless of severity, that leads to discontinuation of study drug, where AE at the injection site is the principal reason for discontinuation.

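### Study drug exposure stops at the last injection, so it is understated by 27, 13 or 6 days depending on regimen and conflicts with the SAP's own treatment period; the dose-intensity denominator is left undefined

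*SAP*

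**What the plan says.** SAP Section 4.5.1 gives one duration formula for every regimen: "Date of last dose – Date of first dose) + 1". The result is summarised in days and in nine categories: up to 13 weeks, 13 to 26 weeks, six 4-week bands from 26 to 50 weeks, and more than 50 weeks.

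The treatment period is defined differently. Below Table 1 in Section 1.2.1, for each cohort, the "treatment period is defined as the time from the first dose through one dosing interval post last dose". Section 4.5.2 uses the same window for on-treatment events: "any TEAE reported during treatment period defined as period from first dose through one dosing interval post last dose".

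Section 4.5.1 also summarises actual dose intensity, "defined as the ratio of total drug received and the actual duration of treatment (in weeks", and relative dose intensity, the ratio of actual to planned. It does not say which of the two definitions gives the duration of treatment, and it does not define planned dose intensity.

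The addendum to SAP version 1.0 redefines percent compliance by volume. It leaves the duration formula and dose intensity as they were.

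**The concern.** An injection given every 4 weeks is meant to cover 4 weeks. A first-to-last-dose span drops the last covered interval except for one day. That would be a harmless convention if all arms shared one short interval. Here the intervals are 28, 14 and 7 days, so the shortfall differs fourfold between regimens that the exposure table sets side by side. Patients treated for the same time and with full adherence appear to have had different exposure.

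Treatment length varies by design between 6 and 12 months, so the exposure table is meant to carry information. A reader who sets on-treatment event incidence beside exposure would see events counted over the longer window and time counted over the shorter one. Pooled placebo combines all three schedules, so its shortfall matches that of no active arm.

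The undefined dose-intensity denominator adds to this. Depending on the reading, a patient who received every dose on time may or may not show 100%.

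**Working it through.** **Inputs.** Section 1.2.1 sets treatment "for up to 52 weekly doses, up to 26 every 2-week doses, or up to 13 every 4-week doses". The 6-month dose counts come from the per-protocol definition in Section 2.1. It asks for "at least 5 out of 6 monthly doses of Study Drug for patients randomized in Cohorts A, B, and C", so 6 doses are planned on the 4-weekly schedule. The same definition counts 13 planned doses in Cohort D (2-weekly) and 26 in Cohort E (weekly).

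**The plan's own figures.** Table 1 totals are dose × number of doses: 20×13 = 260, 40×13 = 520, 60×13 = 780, 20×26 = 520, 20×52 = 1040 mg. All five reproduce. Time covered at maximum dosing is 13×28 = 26×14 = 52×7 = 364 days = 52 weeks, which agrees with the stated maximum treatment period.

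**Exposure under Section 4.5.1.** With *n* doses on schedule at interval *I* days, exposure = (n−1)×I + 1 and the treatment period is n×I. The shortfall is I − 1 whatever the number of doses (I if the end day is also counted).

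| Regimen | Doses | Exposure, days (weeks) | Treatment period, days | Shortfall, days |
|---|---|---|---|---|
| Every 4 weeks | 13 | 12×28+1 = 337 (48.1) | 364 | 27 |
| Every 2 weeks | 26 | 25×14+1 = 351 (50.1) | 364 | 13 |
| Weekly | 52 | 51×7+1 = 358 (51.1) | 364 | 6 |
| Every 4 weeks | 6 | 5×28+1 = 141 (20.1) | 168 | 27 |
| Every 2 weeks | 13 | 12×14+1 = 169 (24.1) | 182 | 13 |
| Weekly | 26 | 25×7+1 = 176 (25.1) | 182 | 6 |

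With equal placebo numbers per cohort (1:1:1:1:1, then 5:1), the average shortfall in pooled placebo is (3×27 + 13 + 6)/5 = 20 days.

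**Categories, courses beyond 26 weeks.**
- Every 4 weeks, 7 to 13 doses: treatment periods of 28, 32, 36, 40, 44, 48 and 52 weeks become 24.1, 28.1, 32.1, 36.1, 40.1, 44.1 and 48.1 weeks. Each drops exactly one category. The 13-dose completer falls in the 46-to-50-week band and would need the last dose at least 14 days late (351 days) to exceed 50 weeks.
- Every 2 weeks, 14 to 26 doses: 2n weeks becomes 2n − 13/7 weeks (28 becomes 26.1, 30 becomes 28.1, and so on to 52 becoming 50.1). None changes category.
- Weekly, 27 to 52 doses: n weeks becomes n − 6/7 weeks. The cut points are whole weeks, so none changes category.

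**Relative dose intensity (RDI).** Suppose actual intensity is divided by the exposure duration and planned intensity is the nominal dose per week. The dose cancels and RDI = n×I / ((n−1)×I + 1).

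| Regimen | 6-month dose count | Maximum dosing |
|---|---|---|
| Every 4 weeks | 168/141 = 119.1% | 364/337 = 108.0% |
| Every 2 weeks | 182/169 = 107.7% | 364/351 = 103.7% |
| Weekly | 182/176 = 103.4% | 364/358 = 101.7% |

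Other readings give other answers:
- Denominator is the defined treatment period: n×I / (n×I) = 100% in every arm at any dose count.
- Exposure duration as denominator, with planned intensity built by the same formula at maximum dosing: 100% for a full course, and 110.3%, 103.8% and 101.7% at the 6-month counts.
- First reading with one mid-course dose missed at 6 months: 140/141 = 99.3%, 168/169 = 99.4%, 175/176 = 99.4%.

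**The case against.** The strongest reply is that these are two named quantities with two definitions. Section 4.5.1 describes exposure as days on which drug was administered, and a first-to-last-dose span is a recognisable measure of that. The on-treatment window for adverse events, and the laboratory shift tables that refer to it, already include the last interval. This stands in part: the formula can be computed, and no safety rate depends on it. It does not remove the regimen-dependent shift in the exposure table, since the same SAP treats the last interval as treatment time.

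The second reply concerns dose intensity, and it stands. A reader might infer that relative dose intensity will exceed 100% as the SAP is written. The text does not support that. Duration of treatment is tied to neither definition and planned intensity is undefined. Even on the reading that gives an excess, the excess shrinks with the number of doses and disappears with one missed dose in a 6-month course. What the document supports is an ambiguity with a computable range.

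A reader might also infer that dose selection or the safety comparison is biased. Section 1.2.1 says the repeated safety analysis serves dose selection, but it does not name exposure duration or dose intensity. Section 4.5.2 reports patient incidence with no exposure-time denominator. Percent compliance by volume and total drug received do not use this duration.

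**Conclusion.** The concern holds for exposure duration. Followed as written, Section 4.5.1 understates on-schedule exposure by 27, 13 and 6 days relative to the SAP's own treatment period. It also moves every on-schedule 4-weekly course beyond 26 weeks down one category while leaving the other two schedules in place. Three of the five active arms would look shorter-treated by definition alone. The day counts are exact for dosing on schedule. Early or late doses shift individual patients, and 2-weekly courses with an even number of doses sit only one day above a category boundary.

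For dose intensity the finding is conditional. A fully dosed 6-month patient on the 4-weekly schedule shows 100% or about 119% depending on a denominator and a planned intensity that the SAP does not fix.

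The effect is confined to descriptive exposure and dose-intensity summaries. Adverse event incidence and the efficacy analyses are untouched. It should be corrected, but it does not threaten the trial's main conclusions.

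**What to change.** In Section 4.5.1, define duration as (date of last dose − date of first dose) + the cohort's dosing interval (28, 14 or 7 days), matching the treatment period in Sections 1.2.1 and 4.5.2. Use it for the duration summary and the categories, and name it as the denominator of actual dose intensity. Define planned dose intensity as dose per dosing interval, expressed per week. On-schedule full courses then give 364 days and 100% relative dose intensity in every arm.

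If duration is cut at death or last contact, apply the cut to the duration summary only. Applied to the dose-intensity denominator, it would bring back very short denominators, and so inflated ratios, for patients who stop early.

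The cost is a wording change and one derived variable, with no new data and no change to trial conduct. Pooled placebo will still mix three schedules, so its weekly intensity remains a mixture and should be read that way.

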#### 4.5.2. Adverse Events

All AEs will be coded using the MedDRA v20.0 coding system and displayed in tables and data listings using system organ class (SOC) and preferred term. Missing and partial dates will be handled as described in [Section 3.10.2](#).

Analyses of AEs will be performed for those events that are considered treatment-emergent, where treatment-emergent is defined as any AE with onset after the first administration of study medication through the end of the study, or any event that was present at baseline but worsened in intensity or was subsequently considered drug-related by the Investigator through the end of the study.

All analyses of TEAEs will be performed on the following periods:

- TEAEs On Study, defined as any TEAE reported after onset of the administration of study medication through the end of the study
- TEAEs On Treatment, defined as any TEAE reported during treatment period defined as period from first dose through one dosing interval post last dose

Adverse events are summarized by patient incidence rates; therefore, in any tabulation, a patient contributes only once to the count for a given AE in both SOC and preferred term.

The number and percentage of patients with any treatment-emergent adverse event (TEAE), with any TEAE assessed by the Investigator as related to treatment (related, possible, unlikely/remove, and not related relationships), with any serious TEAE, and with any treatment-emergent serious AE potentially related to treatment will be summarized by ISIS 681257 treatment group and pooled placebo group. All incidences will also be summarized within each cohort, by ISIS 681257 and placebo.

In addition, AEs will be summarized by relationship to study drug and by severity. In these tabulations, each patient will contribute only once (ie, the most related occurrence or the most intense occurrence) to each of the incidence rates in the descriptive analysis, regardless of the number of episodes.

Three additional TEAE analyses will be performed:

1. Local cutaneous reaction at injection site (LCRIS) defined as either:
  - a. Moderate or severe Injection Site Erythema, Swelling, Pruritus, Pain or Tenderness that started on the day of injection, persisted for at least two days; or
  - b. Any AE at the injection site, regardless of severity, that leads to discontinuation of study drug, where AE at the injection site is the principal reason for discontinuation.
2. LCRIS defined as any AE with preferred term (PT) or verbatim term that contained “injection site” and persisted for at least two days
3. Flu-like reactions (FLR) are defined as either:
  - a. Flu-like illness; or
  - b. Pyrexia or feeling hot or body temperature increased, plus at least two of the following: Chills, Myalgia, and Arthralgia, starting on day of injection or the next day.

The incidences of both LCRIS and FLR will be tabulated by ISIS 681257 treatment group and pooled placebo group, and may be plotted over time if warranted. They will additionally be tabulated within each cohort, by ISIS 681257 and placebo.

No formal hypothesis-testing analysis of AE incidence rates will be performed.

All AEs occurring on-study will be listed in patient data listings.

By-patient listings also will be provided for the following: patient deaths, serious AEs, severe AEs, and AEs leading to withdrawal.

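### SAP Section 4.5.2 defines the treatment-related TEAE row by all four causality levels, including not related, so read literally it repeats the any-TEAE row

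*SAP*

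**What the plan says.** SAP Section 4.5.2 describes an AE overview with four rows.

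1. Any TEAE: "The number and percentage of patients with any treatment-emergent adverse event (TEAE").
2. Any TEAE "assessed by the Investigator as related to treatment (related, possible, unlikely/remove, and not related relationships").
3. Any serious TEAE.
4. Serious and attributed events: patients "with any treatment-emergent serious AE potentially related to treatment will be summarized". No causality levels are listed here.

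The overview is shown for the five ISIS 681257 groups and pooled placebo, and then repeated: "All incidences will also be summarized within each cohort, by ISIS 681257 and placebo". Section 4.5.2 also runs all TEAE analyses for two periods, on study and on treatment.

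A separate output follows: "In addition, AEs will be summarized by relationship to study drug and by severity". In it, "each patient will contribute only once (ie, the most related occurrence or the most intense occurrence").

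Earlier in the same section, the definition of treatment-emergent includes an event present at baseline that "was subsequently considered drug-related by the Investigator through the end of the study".

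**The concern.** The parenthesis in row 2 qualifies the phrase about the Investigator judging the event related, yet its members include the unlikely level and the not-related level. An event judged unrelated cannot belong to the set of events judged related. A programmer who follows the text would count every assessed TEAE, and the row would be labelled as drug-related incidence while showing overall incidence.

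Safety and tolerability stand in the primary objective (Section 1.1.2.1), and Section 1.2.1 says that the safety analysis serves dose selection. The related-TEAE row is one of four overview figures for each regimen. A reader who takes its label at face value would overstate attributed events in every arm, placebo included, and would see no causality contrast in that row beyond the any-TEAE contrast. A programmer who notices the contradiction would have to choose a cut that the SAP does not state.

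**Working it through.** The documents give no AE counts, so this is a check of set membership. There is no figure in the plan to reproduce.

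**Inputs, all from SAP Section 4.5.2**
- Levels listed for row 2: related, possible, unlikely/remove (evidently a slip for remote), not related.
- Row 1: patients with any TEAE.
- By-relationship table: one count per patient, at the most related occurrence.

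**Step 1. Row 2 as written.** Let T be the patients in an arm with at least one TEAE. Let R be those with at least one TEAE whose causality lies in {related, possible, unlikely, not related}. R is always contained in T. If the four levels are the whole scale and every TEAE has an assessment, each TEAE carries one of the four, so T is also contained in R. Hence R = T, and the ratio of row 2 to row 1 is 1.0.

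**Step 2. Where this applies.** The argument does not depend on the arm. It holds in 5 active groups + 1 pooled placebo = 6 groups, on both sides of each of the 5 within-cohort comparisons, and in both the on-study and on-treatment periods. It fails only for patients whose TEAEs all lack an assessment or carry a level outside the four. The SAP gives no rule for a missing assessment.

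**Step 3. Row 2 with a restricted list.** Let R′ use {related, possible}, which is an assumption to be checked against the protocol. R′ is contained in T, so its incidence may lie anywhere from 0 to the any-TEAE incidence. As an illustration with assumed figures: if 80% of an arm has any TEAE and 30% has one judged related or possible, the literal row shows 80% and the restricted row 30%, an overstatement of 80 − 30 = 50 percentage points. The true gap is unknown.

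**Step 4. Can the figure be recovered elsewhere?** In the by-relationship table each patient appears once, at the most related level. The four counts are therefore disjoint. A patient with at least one related or possible TEAE falls in one of the top two levels, and no other patient does. So n(related) + n(possible) = the size of R′. The sum of the two any-event counts gives the missing figure for TEAEs.

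**Step 5. The neighbouring terms, side by side**

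| Place in 4.5.2 | Term | List of levels attached? | Status |
|---|---|---|---|
| Row 2 | related to treatment | Yes, all four | Wrong as written |
| Row 4 | potentially related | No | Undefined |
| TEAE definition | drug-related, as judged by the Investigator | No | Not affected |

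**The case against.** **The parenthesis may only name the scale.** It lists a complete four-level scale and ends on the word relationships, so it could mean one count per level. The slip of remove for remote suggests loose drafting rather than a deliberate cut. This reading is possible but fits poorly. The list qualifies the phrase about events judged related, and the breakdown by level is planned separately, in a sentence that opens by saying it is additional.

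**The information is not lost.** This stands for TEAEs: Step 4 shows that the by-relationship table returns the related plus possible count. In addition, Section 4.5.2 rules out hypothesis tests of AE rates and lists all on-study AEs. A reader might infer that the planned safety output carries no causality information or cannot compare the regimens on attributed events. The documents do not support that, because the defect is confined to one row.

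**The other two terms do not use the list.** This also stands. A reader might infer that the potentially related serious-AE row includes unrelated events, or that a pre-existing event judged not related would become treatment-emergent. Neither follows. The serious-AE row carries no list, and the TEAE definition rests on the Investigator's own judgement without pointing to the later parenthesis.

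**The protocol may define causality.** It may, and the absence of a cut from the SAP would not by itself be a finding. A protocol definition would not, however, correct a list in the SAP that contradicts its own label.

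**Conclusion.** The point holds for one row. Taken literally, the related-TEAE row in Section 4.5.2 equals the any-TEAE row in all six groups and in every within-cohort comparison, so it would be a mislabelled safety figure. Exact equality rests on two assumptions: that the four levels are exhaustive, and that no causality assessment is missing. The size of the overstatement cannot be computed from the document. It lies between zero and the whole any-TEAE incidence.

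The consequence is modest. The figure can be rebuilt from the by-relationship table, no test uses it, and no efficacy inference is touched. For serious AEs the SAP promises no specific breakdown by relationship, so settling the undefined term there has some value of its own. The correction is nevertheless worth making, because a stated rule gives the wrong number in a headline tolerability row and the remedy costs almost nothing.

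**What to change.** Before unblinding, amend Section 4.5.2 as follows.

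- Restrict the parenthesis in the related-TEAE row to the levels that count as related. Related and possible are the natural choice, to be checked against the protocol's causality definitions.
- Use the same cut for the potentially related serious-AE row.
- State how a missing causality assessment is counted, for example as related, again in line with the protocol.
- Correct remove to remote.
- Keep the four-level by-relationship table unchanged.

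This is a matter of a sentence or two in the SAP and needs no new data. The one downside is that the related row will show a smaller figure than the literal text would give.
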